- a. Data analysis: Data analysis will be performed primarily by the PI at Columbia University. The primary analysis will use paired t-tests to compare pulmonary microvascular blood flow on aspirin compared to placebo, and CD31⁺ EMPs on AAT augmentation therapy compared to off augmentation following the intention-to-treat principle. Similar analyses will be performed for secondary endpoints. Exploratory analyses will also evaluate for different effects in subgroups by smoking status, COPD severity, use of supplemental oxygen, and by severity of reduction in DLCO and will evaluate for period and carryover effects. Approaches to missing data will include: 1) minimization through short study duration and efforts to retain 100% of participants for 3 months and 2) sensitivity analyses using a variety of imputed values (worst-case scenario, baseline observation carried forward, last observation carried forward).
- b. Statistical power: Power was estimated for a paired t-test to compare an individual's pulmonary microvascular blood flow before and after the intervention. For 15 subjects with power of 80% and $\alpha=0.05$, we will be able to detect a minimally significant difference of 0.30 log CD31⁺ EMPs (1.2 SDs of the difference in log CD31⁺ EMPs for those on replacement and not), and a minimally significant difference of 48.4 mL blood/min*100mL lung (1.6 times the SD of the difference in pulmonary microvascular blood flow [PMBF] for those on replacement and not). Power will be adequate for CD31⁺ EMPs and moderate for PMBF. As power was derived from a cross-sectional analysis, this is a conservative estimate and we expect that power will be improved when comparing changes within an individual.

4. Recruitment and Consent

- a. Recruitment: Participants will be recruited from multiple sources. First, we will recruit among the 30 participants who previously enrolled in the Alpha-1 extension of the MESA COPD Study over the telephone (AAAD6395). All of these participants agreed to be contacted for future research purposes on their consent forms. Second, we will email,

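### Section 3.b: a paired t-test with 15 subjects has 80% power at 0.78 SD of the difference, not at the stated 1.2 and 1.6 SD

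*Combined protocol and SAP*

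**What the plan says.** Section 3.b (Statistical power) opens: "Power was estimated for a paired t-test to compare" PMBF within an individual before and after the intervention. The conditions follow: "For 15 subjects with power of 80% and" alpha 0.05. Sidedness is not stated.

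Two detectable differences are given under those conditions:

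- CD31+ EMPs: 0.30 log units, described as "1.2 SDs of the difference in log CD31"+ EMPs between people on replacement and not.
- PMBF: "a minimally significant difference of 48.4 mL blood/min*100mL lung (1.6 times the SD of the difference in pulmonary microvascular blood flow", again for people on replacement and not.

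The paragraph then grades the result: "Power will be adequate for CD31"+ EMPs and moderate for PMBF. On the source it says "As power was derived from a cross-sectional analysis, this is a conservative estimate", and adds that "we expect that power will be improved when comparing changes within an individual".

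Section 3.a specifies the matching analysis for PMBF: "The primary analysis will use paired t-tests to compare pulmonary microvascular blood flow on aspirin compared to placebo". CD31+ EMPs are compared by the same test, on versus off augmentation.

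**The concern.** Once the number of pairs, the power and alpha are fixed, a paired t-test has one detectable difference in units of the SD of the within-person difference. It does not depend on the endpoint. Two different multiples under the same conditions and the same label therefore signal an error before anything is calculated.

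This paragraph is the plan's only statement of what 15 subjects can detect on the two primary endpoints. If its figures do not follow from the test it names, a reader cannot check whether power is adequate, moderate or conservative, and anyone planning a later trial from 48.4 mL or 0.30 log would inherit a figure with no clear basis.

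A related weakness is that the PMBF SD is taken from people on versus not on replacement, while the primary PMBF comparison is aspirin versus placebo.

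**Working it through.** **Inputs (section 3.b).** Paired t-test, n = 15, power 80%, alpha 0.05; 0.30 log = 1.2 SD; 48.4 mL = 1.6 SD. Two-sided testing is my assumption; one-sided results are also shown.

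**1. Attempt to reproduce the plan's multiples.** Power is taken from the noncentral t distribution with df = n − 1 = 14 and noncentrality d√n, where d is the difference divided by the SD of the within-person difference. Solving for 80% power:

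- two-sided: d = 0.778
- one-sided: d = 0.675

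Neither 1.2 nor 1.6 is reproduced.

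**2. Power at the plan's multiples (paired, two-sided).**

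| Multiple | Power at n = 15 | Smallest n for 80% | Power at that n | Power at n − 1 |
|---|---|---|---|---|
| 1.2 SD | 99.1% | 8 | 82.8% | 75.4% |
| 1.6 SD | over 99.9% | 6 | 87.5% | 76.2% |

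**3. If the implied SDs are paired-difference SDs (assumption).** The implied SDs are 0.30/1.2 = 0.25 and 48.4/1.6 = 30.25. The detectable differences become:

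- CD31+ EMPs: 0.778 × 0.25 = 0.19 log (0.18 to 0.21 allowing for rounding in the plan's figures)
- PMBF: 0.778 × 30.25 = 23.5 mL (22.8 to 24.3 allowing for rounding)

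**4. If 0.30 and 48.4 are right (assumption).** The SDs of the difference must then be 0.30/0.778 = 0.39 and 48.4/0.778 = 62 two-sided, or 0.44 and 72 one-sided.

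**5. If the quoted SDs are between-person SDs (assumption).** The cross-sectional source points this way. The SD of the difference is then √(SD_on² + SD_off² − 2ρ·SD_on·SD_off).

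- Equal SDs: the multiple is 0.778 × √(2(1 − ρ)), which is 1.10, 0.78 and 0.55 at ρ = 0, 0.5 and 0.75. With ρ ≥ 0 it never exceeds 1.10. Applied to 30.25 and 0.25, these multipliers give 33.3, 23.5 and 16.6 mL, and 0.28, 0.19 and 0.14 log.
- Unequal SDs, ratio r, expressed in units of the smaller SD: the multiple is 0.778 × √(1 + r² − 2ρr). Reaching 1.2 and 1.6 requires r = 1.17 and 1.80 at ρ = 0, 1.51 and 2.12 at ρ = 0.3, and 1.78 and 2.37 at ρ = 0.5. The plan reports no such SDs.

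**6. If an unpaired test was used (not the stated test).** For 15 people in total with equal SDs (df = 13), the two-sided difference at 80% power is 1.57 SD for a 7 versus 8 split, 1.60 for 6 versus 9, 1.66 for 5 versus 10, and larger for more uneven splits. The one-sided minimum is 1.36. So 1.6 can be approached, but 1.2 cannot: two-sided power at 1.2 SD is 57% for 7 versus 8 and 56% for 6 versus 9, against 81.5% and 80.1% at 1.6 SD.

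**The case against.** The strongest reply is that the SDs were never meant as paired-difference SDs. The plan says they come from cross-sectional data on people on and not on replacement. With a between-person denominator the multiple need not be 0.78 and need not agree across endpoints; at zero correlation, SD ratios of 1.17 and 1.80 reproduce 1.2 and 1.6 exactly. On that view 0.30 and 48.4 may be sound and only the label is loose. It can also be said that the check on unpaired tests covers only totals of 15: section 4.a mentions 30 earlier participants, and a split of 8 versus 22 gives 1.20.

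Much of this stands. The documents do not show that 0.30 or 48.4 is wrong, and the power figures of 99% and above apply only to the literal reading of the label. But the reply relocates the error and does not remove it: if the SDs are between-person, calling them SDs of the difference under a paired test is the mistake. The SD ratios needed are not reported, and 8 versus 22 is neither 15 subjects nor paired.

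The consequence is also limited. The sample size of 15 is an input to the calculation, the plan itself warns that its source is cross-sectional, and if the implied SDs are paired-difference SDs the error is in the safe direction.

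**Conclusion.** The concern holds. As written, 1.2 and 1.6 SDs of the difference do not follow from a paired t-test with 15 subjects, 80% power and alpha 0.05; the correct multiple is 0.78 two-sided or 0.68 one-sided, for both endpoints. This rests only on the conditions stated in section 3.b.

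Which element is wrong cannot be settled from the documents, because neither raw SDs nor a within-person correlation is given. The two main readings differ by a factor of about two for PMBF (48.4/23.5) and about 1.5 for CD31+ EMPs (0.30/0.19). Between-person SDs would give other values again. The statements about adequate, moderate and conservative power therefore cannot be verified; nor does section 3.b explain why two differences both stated at 80% power are graded differently.

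This should be fixed, but it does not undermine the trial: the primary analyses, the sample size and the reading of the completed trial from its own confidence intervals are unaffected.

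**What to change.** Restate section 3.b on a single basis. Suggested wording:

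> With 15 completers, a paired t-test (two-sided alpha 0.05) has 80% power to detect 0.78 SD of the within-person difference. For log CD31+ EMPs (on versus off augmentation) the SD used is [value; source; between-person or of a within-person difference], giving [value]. For PMBF (aspirin versus placebo) the SD used is [value; same details], borrowed from people on versus not on replacement, giving [value].

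- If only between-person SDs exist, compute the SD of the difference from both group SDs with the formula in step 5 over a range of ρ, for example 0, 0.5 and 0.75, then multiply by 0.78. The shortcut multipliers 1.10, 0.78 and 0.55 apply only when the two SDs are equal.
- If a one-sided or an unpaired test was intended, say so and recompute.
- Do not insert 0.19 log or 23.5 mL unless 0.25 and 30.25 are confirmed as paired-difference SDs.
- Revise the descriptions of power to agree with the recomputed figures.

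The cost is one paragraph of protocol text and retrieval of the source SDs (both group SDs if they are between-person). Sample size, procedures and primary analyses stay as they are.

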Successful completion of these aims would demonstrate that aspirin and AAT augmentation therapy improve pulmonary microvascular blood flow and reduce CD31⁺ EMPs in AATD-related lung disease, would support future studies evaluating aspirin in emphysema in AAT, demonstrate additional benefits of AAT augmentation, and support the use of pulmonary MRI and EMPs as outcomes for clinical trials in COPD.

2. Study Design

- a. The proposed study is a single-center Phase IIa randomized cross-over study and withdrawal study.
- b. The study will accrue 15 subjects and enroll up to 20.
- c. Inclusion criteria:
 - i. Alpha-1 antitrypsin deficiency (PiZZ genotype)
 - ii. 40 years of age or older
 - iii. Evidence of emphysema on CT scan as read by a Radiologist
 - iv. On intravenous alpha-1 antitrypsin replacement therapy
- d. Exclusion criteria:
 - i. Platelet count < 150,000/dL, history of intracranial hemorrhage or severe GI bleed, use of systemic anticoagulant, physician prescribed use of antiplatelet drug (including aspirin and P2Y12 receptor inhibitors), or known severe liver disease;
 - ii. Immunosuppression by use of medications (including oral prednisone) or medical condition (organ transplantation or actively-treated malignancy), including autoimmune conditions that require immunomodulatory treatment (e.g. anti-TNF agents);
 - iii. Known atrial fibrillation or left ventricular (LV) systolic heart failure;
 - iv. Contraindication to MRI, including pregnancy, weight > 300 lbs (due to weight limits of the machine), those with pacemakers, aneurysm clips, cochlear implants or other implanted electronic devices, or severe claustrophobia;

- v. Chronic renal insufficiency (estimated GFR < 45 L/min/1.73 m² or self report) due to slightly increased risk of nephrogenic systemic fibrosis from gadolinium administration and aspirin-related renal insufficiency. GFR will be calculated using the MDRD equation based on the most recent laboratory sample available (within the last 30 days required). If one is not available at the time of MRI a point-of-care Creatinine will be run and this value will be used instead of the laboratory sample;
- vi. Frequent exacerbations of respiratory symptoms (two or more in the last year); and
- vii. Exacerbation of respiratory symptoms within the previous 6 weeks, such as that requiring hospitalization, oral prednisone or antibiotics to control symptoms.

[figure not shown]

Figure 1. Study Design

Table 1: Study Components

Visit #:	1	2	3	4

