 - f. Subjects will undergo telephone pre-screening before Visit 1. At Visit 1 they will be consented, after which a platelet count and creatinine will be drawn to confirm eligibility. Participants will then complete questionnaires, perform spirometry, diffusing capacity and pulse oximetry. Eligible patients will then be randomized as to the order of intervention vs. placebo and will undergo non-contrast chest CT. Randomization will be stratified by smoking status with full concealment of allocation; subjects and the investigative team will be blinded as to treatment assignment. The intervention will be 81mg aspirin and a matched placebo, each taken once per day in the morning. Each treatment will last approximately 2 weeks (Figure 1, previous page) with Visits 2 and 3 occurring at the end of treatment 1 and 2, respectively. Each treatment may be continued for up to 18 days, if needed, to coordinate scheduling of the participant visit and procedures. There will be a 2-week washout period between the treatments, and the total length of the randomized protocol will be approximately 6 weeks. The CU Research

Pharmacy will dispense study medications. During the study period, subjects will be asked to continue the same medication regimen and avoid using over-the-counter aspirin and other non-steroidal anti-inflammatory drugs.

- g. Timing with respect to AAT infusions: We will recruit subjects who are on AAT augmentation therapy, and the timing of study visits will be coordinated with their weekly dosing of AAT to minimize differences between study visits other than the intervention. We will schedule patient visits on days 1-3 post-infusion in order to study the effects of peak AAT levels.
- h. Withdrawal of AAT augmentation therapy:
Subjects will be asked to stop AAT augmentation therapy for approximately 5 weeks and return for Visit 4. Withdrawal of AAT for 5 weeks (a maximum of 5.5 weeks) will allow AAT levels to drop briefly to those seen in the absence of AAT augmentation.

3. Statistical Procedures

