call, meet in person with, or mail flyers to pulmonologists within the recruitment region who see patients with alpha-1 antitrypsin deficiency to ask them to refer any patients who might be interested. The flyer may also be posted on the pulmonary and lung transplant floors of Presbyterian Hospital at Columbia University. Third, we will distribute study information through AlphaNet, a network for Alpha-1 patients that is affiliated with the Alpha-1 Foundation (see attached recruitment materials). Fourth, we will utilize the Alpha1 Research Registry (run out of the Medical University of South Carolina), who maintains a database of approximately 5,000 persons with alpha-1 antitrypsin deficiency and can send study information to a subset who meet our basic eligibility criteria and live in the geographic region. Fifth, we will contact leaders of support groups for alpha-1 antitrypsin deficiency in the recruitment region to consider presenting material about our study at their meetings, allowing us to present the material, or distributing recruitment materials to their list-serve via email. The recruitment region includes NY, NJ, CT, PA, DE and MA.

Interested persons will be contacted directly by telephone to discuss the study (following the attached script). The interviewer will then administer a Screening Questionnaire to check inclusion and exclusion criteria, and determine willingness to participate.

For persons who are screened over the telephone but found to be ineligible for the study, we will keep record of their name, telephone number and Screening Questionnaire for the duration of the study in a locked cabinet in the study coordinator's office. The rationale for this is 1) to ensure that we do not contact the same person twice, and 2) in the event that we change eligibility criteria, we would be able to contact the appropriate persons for potential inclusion in the study. We will send an information sheet to those who are screened but ineligible to inform them that they were contacted for this study.

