on augmentation therapy compared to those not on augmentation therapy;⁴⁰ a meta-analysis of randomized and non-randomized studies found a slower rate of FEV₁ decline in those with initial FEV₁ between 30-65% predicted who were on augmentation therapy compared to those not on therapy;⁴¹ and a retrospective study found lower exacerbation rates and less severe exacerbations in subjects when they were on augmentation therapy compared to when they were not on augmentation therapy.⁴² A few RCTs have also found a borderline reduction in the progression of CT emphysema in those on AAT augmentation compared to those not,⁸⁻¹⁰ with one meeting statistical significance.¹¹ One of these RCTs evaluated exacerbations in 77 participants over 2 years, they found the overall exacerbation rate to be similar among the two groups, however a post-hoc analysis found a reduction in severe exacerbations (those requiring hospitalization) in those on augmentation therapy.⁹ In summary, there is no data to suggest that short term withdrawal of AAT augmentation will lead to a clinical change or exacerbation. The participants in this study will miss approximately 4 doses of AAT augmentation over approximately 5 weeks (5.5 weeks maximum), this is 1/24 of the 2-year duration of the RCT mentioned above and there would be little change in emphysema or exacerbation rates expected to occur during this interval. However, we will mitigate the potential risk of increased exacerbations during this short withdrawal period by excluding participants who have experienced frequent exacerbations (2 or more exacerbations in the last year).

b. Study Procedures

- i. Anthropometry, blood pressure and pulse oximetry. There are no direct risks or discomforts from participation in the anthropometry, blood pressure or pulse oximetry to measure oxygen saturation.
- ii. Questionnaires. There is minimal risk related to questionnaires, this involves the social-psychological risk from the inadvertent disclosure of confidential medical information. We guard against this by maintaining study information identified by study number only in a filing system separate from the name and address files.

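### The exacerbation exclusion that is meant to protect participants while AAT is withheld is checked only at entry, about 42 to 50 days before AAT is stopped

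*Combined protocol and SAP*

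**What the plan says.** Section 7.a.iii describes AAT replacement as the US standard of care. It names one mitigation for exacerbation risk while AAT is withheld: "we will mitigate the potential risk of increased exacerbations during this short withdrawal period by excluding participants who have experienced frequent exacerbations". The matching exclusion, 2.d.vi, reads "Frequent exacerbations of respiratory symptoms (two or more in the last year". Exclusion 2.d.vii adds an exacerbation within the previous 6 weeks.

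Section 4.a describes the telephone check before Visit 1: "The interviewer will then administer a Screening Questionnaire to check inclusion and exclusion criteria". For Visit 1, section 2.f says that consent is taken, "after which a platelet count and creatinine will be drawn to confirm eligibility". It names no exacerbation item there.

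The crossover follows. Section 2.f says "the total length of the randomized protocol will be approximately 6 weeks" and also "Each treatment may be continued for up to 18 days, if needed, to coordinate scheduling of the participant visit and procedures", with a 2-week washout between treatments. Section 2.h then says "Subjects will be asked to stop AAT augmentation therapy for approximately 5 weeks and return for Visit 4". It sets no condition for starting the withdrawal.

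**The concern.** The safeguard is a history taken at one time, and the exposure it is meant to cover starts at another. A person with one exacerbation in the year before entry is eligible. If that person has a second during the crossover, they can meet 2.d.vi when AAT is stopped. Anyone with an exacerbation shortly before Visit 3 meets 2.d.vii at that point, whatever their earlier history. Nothing in the supplied text prevents withdrawal in either case.

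What is at stake is who has standard-of-care therapy withheld for about 5 weeks. The validity of the aspirin comparison is not at issue.

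**Working it through.** **Interval between check and exposure.** From 2.f, the nominal crossover is 14 + 14 + 14 = 42 days, which reproduces the stated 6 weeks. The maximum is 18 + 14 + 18 = 50 days. Both run from the start of treatment 1, so time between telephone screening and first dose adds to them. The look-back in 2.d.vii is also 42 days, so the window examined at entry has fully elapsed by the time AAT can be stopped.

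**What is re-checked after entry.**
- Creatinine is repeated at visits 2-4 (section 5, item 4).
- MRI contraindications are asked before MRI, and women aged 40-55 have a pregnancy test before scanning (section 5, items 10 and 11).
- Section 7.b.vi has an 8-week symptom look-back, but it governs only the walk test.
- Questionnaires at visits 1-4 cover respiratory symptoms and medication (section 5, item 3), with no decision rule attached.

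None of these is tied to stopping AAT.

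**How many might newly meet 2.d.vi.** The documents give no exacerbation rate. I assume r = 0.25, 0.5 or 1.0 per person-year (364 days), constant, among people admitted with at most one event in the last year.

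P(one prior event, given at most one) = r/(1+r) = 0.20, 0.33, 0.50.
P(at least one event in d days) = 1 − exp(−r·d/364).
P(newly meets 2.d.vi) is the product of the two.

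| r | d | P | expected of 15 | at least one of 15 |
|---|---|---|---|---|
| 0.25 | 42 | 0.57% | 0.09 | 8% |
| 0.5 | 42 | 1.87% | 0.28 | 25% |
| 1.0 | 42 | 5.45% | 0.82 | 57% |
| 0.25 | 50 | 0.68% | 0.10 | 10% |
| 0.5 | 50 | 2.21% | 0.33 | 28.5% |
| 1.0 | 50 | 6.42% | 0.96 | 63% |

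**Stricter counts at 42 days.** This version requires no event in the 6 weeks before entry, lets earlier events age out of the one-year window, and counts two crossover events. It gives 0.07, 0.24 and 0.72 of 15. If individual rates also vary (gamma, shape 1 or 2, simulated), the result is about 0.09, 0.23-0.24 and 0.46-0.56 of 15. The lower rates hardly move, but the top-rate figure drops by a third or more.

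**How many would meet only 2.d.vii.** Among people with a crossover exacerbation, the share with no event in the year before entry is 1/(1+r) = 80%, 67%, 50%. At 42 days, 15 × (1 − exp(−r·42/364)) = 0.43, 0.84 and 1.63 participants have a crossover exacerbation. Of these, 0.34, 0.56 and 0.82 meet only 2.d.vii (a second crossover event is ignored). A re-check of 2.d.vi alone would miss them.

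**Can the check come before a missed dose?** Dosing is weekly, and section 2.g says "We will schedule patient visits on days 1-3 post-infusion". The next dose after Visit 3 is therefore due 7 − 3 = 4 to 7 − 1 = 6 days later, so it can.

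**Price of a lost pair.** Two-sided paired t-test, alpha 0.05, noncentral t, 80% power:
- n = 15: 0.778 SD.
- n = 14: 0.810 SD, and power at 0.778 SD is 76.8%.
- n = 13: 0.847 SD, and power at 0.778 SD is 73.1%.

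Section 3.b quotes 1.2 SD for CD31+ EMPs and calls its power basis cross-sectional. The figures here serve only to price a lost pair.

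**The case against.** The strongest reply is that 2.d.vi is an entry criterion used to select a lower-risk group. Section 7.a.iii does not promise that nobody will cross the threshold later. After 42 days, 322/364 = 88% of the one-year look-back is unchanged. This stands: a reader might infer that the plan breaches its own rule, and the documents do not support that.

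A reader might also infer that the plan checks eligibility only once. It does not, because renal function, MRI contraindications and pregnancy are checked again for imaging. Only the exacerbation criteria lack a later check.

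The benefit is small. The same section expects little change in exacerbation rates over this interval. It also reports that a 2-year RCT found similar overall rates, with fewer severe exacerbations only post hoc. As an illustration, assume an affected person has 2 exacerbations a year and withdrawal doubles that for 35 days. The extra is 2 × 35/364 = 0.19 per person, so sparing 0.09, 0.28 or 0.82 people averts about 0.02, 0.05 or 0.16 events per trial. This stands too.

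The Data Safety and Monitoring Plan is a separate document that was not available, and Figure 1 is not shown. Either could contain the missing rule, so its absence from the whole plan is not established.

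Finally, Visit 3 already collects symptoms, medication, spirometry, diffusing capacity and oximetry, and partial participation is allowed (4.b). The information is therefore at hand, but no rule connects it to the decision to stop AAT.

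**Conclusion.** The point holds in a limited form. In the supplied text, the exacerbation criteria are applied only at entry, and AAT is stopped 42 to 50 days later without a re-check. A participant may then meet 2.d.vi or 2.d.vii when therapy is withheld.

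Under the assumed rates, fewer than one participant in 15 is expected to newly meet 2.d.vi in every scenario. The 57% and 63% chances of at least one belong to the top rate under the simpler model and should be read as upper figures.

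A reader might infer excess harm from withdrawal or bias in either comparison; nothing in the documents shows either. This is a minor, optional safety improvement, justified because the plan's own safeguard can be applied when it is needed at little cost.

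**What to change.** In 2.h, re-apply 2.d.vi and 2.d.vii at Visit 3, before the next weekly dose is missed, by adding the exacerbation items of the Screening Questionnaire to the Visit 3 questionnaire.

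- A participant who meets 2.d.vi does not have AAT withheld and contributes to the aspirin RCT only.
- A participant who meets only 2.d.vii continues AAT, and withdrawal is deferred until 6 weeks after the exacerbation.
- If AAT is stopped later than the first dose due after Visit 3, ask the items again by telephone on the stop date.

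In 3.a, state that participants who never start withdrawal are left out of the paired on/off CD31+ comparison, and report their number. Without this, the carried-forward sensitivity analysis in 3.a could put an on-AAT value in the off-AAT slot and imply no effect.

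If the Data Safety and Monitoring Plan already contains the check, cite it in 2.h and 7.a.iii instead.

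Cost: a few sentences, using an existing visit and questionnaire. The aspirin comparison loses nothing, because the check follows its last measurement. The check precedes withdrawal, so it does not select on a withdrawal effect. The withdrawal comparison may lose about one pair (0.78 to 0.81 SD, or power 80% to 77%). At the top assumed rate under the simpler model, two or more are lost in about 20% of trials. The enrolment limit of 20 in 2.b leaves room to replace them. Some withdrawals are delayed, which lengthens the gap between the on-AAT measurement and Visit 4.
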